6.4 Multiplicity

No adjustments for multiplicity will be performed.

7 Subject Disposition

7.1 Disposition of Subjects

The number of subjects screened, randomized, randomized and treated, randomized and not treated, and the number of subjects in the analysis populations will be summarized.

The number and percentage of subjects will also be summarized for the following subject disposition categories:

- Completed study drug treatment per protocol
- Discontinued study drug early and the reason for discontinuation
- Completed the study including follow-up period
- Discontinued from the study early and the reason for discontinuation

7.2 Important Protocol Deviations

As a guideline, important protocol deviations (IPDs) are:

- Non-compliance with study drug
- Pregnancy
- Other deviations that violate inclusion or exclusion criteria
- Outside Study Windows

The occurrence of protocol deviations will inform which subjects to include in the Per Protocol population.

The Per Protocol population must be finalized prior to the post-freeze data review meeting (or earlier), prior to database lock

Subjects indicating reason for discontinuation at end of treatment visit as Other Protocol Deviation will be listed along with their deviation reason, demographics and study drug group for inclusion in the CSR based on the deviation data entered into CTMS.

7.3 Extent of Study Drug Exposure and Compliance

Exposure to study drug, number of days dose is taken and compliance with study drug dosing will be summarized by treatment group using the Safety Population. Study drug accountability including bottle types, dispensed tablets and returned tablets will be listed. Study drug not returned will be assumed to have been taken.

Study drug compliance will be calculated using values from the Study Drug Accountability and Exposure – Oral CRF pages as shown below:

$$(\text{Number of Tablets Dispensed} - \text{Number of Tablets Returned}) / (\text{End Date} - \text{Start Date} + 1)$$

Percentage of subjects meeting Study Drug Compliance will be presented in the following categories: at least 85% of dispensed tablets (coded as yes/no), and, < 80%, ≥ 80% to < 85%, ≥ 85% to < 90%, and ≥ 90%.

8 Demographic and Baseline Characteristics

8.1 Demographic and Baseline Characteristics

Baseline data will be summarized for continuous and categorical variables as applicable.

The following subject demographics and pre-dose values will be summarized in the Full Efficacy population:

- Age, and Age group (< 45 years, 45 to < 65 years, and \geq 65 years);
- PBC Diagnosis Age, and PBC Diagnosis Age group (<45, \geq 45)
(Age at diagnosis will be calculated as [year of diagnosis] minus [year of birth]. If only the subject's age at screening is available (rather than year of birth), then [year of signing consent (first consent)] minus [age at consent] will be used in place of [year of birth]);
- Duration of PBC, and Duration of PBC category (<7.5 years vs \geq 7.5 years);
- Sex, and Females of Child-Bearing Potential;
- Ethnicity, Race;
- Height, Weight, BMI;
- liver stiffness score;
- documented fibrosis stage;
- UDCA usage (Yes/No), UDCA Total Daily Dose (will be derived as the total daily dose recorded immediately prior to first dose of study drug - as an ongoing concomitant medication at that time; any changes in UDCA use are not expected and will not affect the derivation of this baseline characteristic);
- UDCA response status;
- ApoE Isoform (Genomics) as resulted at Day 1, if no Day 1 value is present reported as the next result available in the progression of study visits (i.e. Day 1, Week 2, Week 4, Week 8, Week 12, and EOS);
- Alkaline phosphatase (ALP): screening value, baseline (last pre-dose) value, average of all pre-dose values;
- Alanine Aminotransferase (ALT);
- Conjugated (direct), Unconjugated (indirect), and Total Bilirubin (unconjugated will be derived as total minus conjugated).
- Gamma-Glutamyl Transferase (GGT)

No statistical testing will be performed on the aforementioned demographic data.

8.2 Medical History

Subjects medical history will be summarized by treatment group for all subjects in the safety population. Medical history data will be coded using MedDRA 20.1 and summarized by system organ class and preferred term. No inferential testing will be performed in this section.

8.3 Prior and Concomitant Medications

Subjects taking UDCA at the start of the study must remain on the same dose of UDCA throughout the 12-week dosing period. Subjects who were not taking UDCA at the start of the study will not be allowed to initiate treatment during the study. Subjects will be classified as taking or not taking UDCA.

Medications will be categorized by medication group and subgroup according to WHODRUG (Version Global B3 2017SEP01 DDE+HD (Enhanced + Herbals)). Refer to the Coding Conventions document for this study.

A medication will be considered concomitant if started or continued to be taken after first dose of study drug through 30 days after the last dose of study drug. Otherwise if a medication was stopped prior to first dose of study drug then it will be considered prior.

Prohibited medications are inhibitors and inducers of CYP3A4 and P-gp (taken between 14 days prior to first dose through 30 days after last dose of study drug). Any medication that inhibits or induces the transporter proteins P-gp are also prohibited during the study. Use of a new statin regimen is prohibited from Screening and throughout study duration. Additional details of prohibited medications please see protocol section 5.9. For protocol restrictions other than prohibited medications, please see the protocol section 5.10

In order to flag prohibited medications taken in the study, each medication taken will be compared against a pre-specified list of all prohibited medications. Prior, Concomitant and Prohibited medications will be summarized based on the number and percentage of subjects using each medication along with the number and percentage of subjects using at least one medication within each medication group and subgroup.

Prior, concomitant, and prohibited medications will be summarized for the Safety Population. All medications will be listed per subject.

9 Efficacy Analysis

The variables from the data to be used to produce the analysis of the objectives and corresponding endpoints are presented below. All efficacy endpoints will be evaluated using the Full Efficacy population.

9.1 Primary Endpoint

9.1.1 Definition of Primary Endpoint

The primary endpoint is defined as the proportion of subjects who have either a 20% reduction in ALP from pre-treatment values or normalization of ALP at Week 12. All subjects in the Full Efficacy population will be included in the analysis of the primary endpoint. Meeting either of these conditions will be considered meeting the primary endpoint of ALP response. Subjects who are missing either Baseline or Week 12 ALP results cannot have either condition evaluated, and will therefore be counted as failure (non-responder). Subjects having both Baseline and Week 12 ALP results will each be evaluated as follows:

1. Percent change will be calculated as $[(ALP \text{ at Week 12} - ALP \text{ at Baseline}) / ALP \text{ at Baseline}] * 100$. The subject will be considered to have successfully achieved 20% reduction in ALP if the result is ≤ -20 .
2. The subject will be considered to have successfully achieved ALP normalization if ALP was abnormal at baseline and normal at week 12.

If either condition is met, the subject is a responder (ALP Response = YES); if the subject fails both conditions, the subject is a non-responder (ALP Response = NO). The proportion of subjects with a 'Yes' for ALP Response will be compared among the 3 study treatment groups. The denominator for this calculation is the number of subjects in the Full Efficacy population.

9.1.2 Analysis of Primary Endpoint

For the primary endpoint, the Cochran-Mantel-Haenszel (CMH) test will be used to compare the proportion of subjects with ALP Response = "Yes" (percent improvement < -0.20 and/or normalization at Week 12 from Baseline) for each of the active treatment groups to placebo. The CMH test will be stratified, two-sided with an alpha level at 0.05. For the stratification in this analysis, the two randomization strata (fibrates and UDCA use) will be combined to create one strata variable. The code used to generate the p-value for each active treatment vs the placebo will be (with necessary output steps added):

Proc freq data=*indata*;

Tables strata*treatment*response/cmh;

Run;

The primary analysis of the primary endpoint will be performed using the Full Efficacy population. The analysis will be repeated on the Per-Protocol (PP) population, including only subjects with Baseline and Week 12 ALP results.

Subgroup analysis will be performed for ALP Response for the following subgroups:

- Age (<65 vs ≥65)
- gender
- UDCA strata
- Prior use of Fibrates strata
- ALP baseline categories [1.67xULN,2xULN), [2xULN,3xULN), [3xULN,4xULN), [4xULN,5xULN), and ≥5xULN (categories are data dependent)
- Total Bilirubin baseline categories [1xULN,2xULN), [2xULN,3xULN), ≥3xULN (categories are data dependent)
- ALP/Total Bilirubin/UDCA baseline subgroup (categories are data dependent, cut points should be based on median baseline values)
 - ALP≤3xULN, Total Bilirubin≤2xULN, UDCA usage,
 - ALP≤3xULN, Total Bilirubin>2xULN, UDCA usage
 - ALP>3xULN, Total Bilirubin≤2xULN, UDCA usage,
 - ALP>3xULN, Total Bilirubin>2xULN, UDCA usage
 - ALP≤3xULN, Total Bilirubin≤2xULN, No UDCA usage,
 - ALP≤3xULN, Total Bilirubin>2xULN, No UDCA usage
 - ALP>3xULN, Total Bilirubin≤2xULN, No UDCA usage,
 - ALP>3xULN, Total Bilirubin>2xULN, No UDCA usage

The code used to generate the p-value for each active treatment vs the placebo will be:

Proc freq data=*indata*;

Tables *subgroup**treatment*response/cmh;.

Run;

The subgroup analysis will be performed using the Full Efficacy population

The proportion of responders will be summarized and plotted by Visit.

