This plan is a living document that is created during the study start-up. The SAP will be drafted within three months of final CRF and maintained throughout the lifecycle of the study. The SAP will be amended with any changes that occurred during the course of the study and finalized prior to database lock. The SAP and amended SAP will be approved and signed off by the Project Manager and the Sponsor.

The SAP outlines the following:

- Study objectives
- Study design
- Variables analyzed and analysis populations
- Applicable study definitions
- Statistical methods regarding important protocol deviations, study drug exposure, efficacy analysis, concomitant medications, adverse events handling, laboratory data and physical examinations
- Study conduct methods for maintaining blinding of efficacy lab data during the course of the study

3 Introduction

This SAP describes the statistical methods to be used during the reporting and analyses of data collected under Enanta Pharmaceuticals, Inc.'s Protocol EDP 305-201, titled "A Phase 2 Dose Ranging, Randomized, Double Blind, Placebo-Controlled Study Evaluating the Safety, Tolerability, Pharmacokinetics and Efficacy of EDP-305 in Subjects with Primary Biliary Cholangitis (PBC) with or without an Inadequate Response to Ursodeoxycholic Acid (UDCA)." The study protocol provides conduct for a phase 2 randomized, double blind, dose-ranging placebo-controlled study to evaluate the safety, tolerability, efficacy, and pharmacokinetics of compound EDP-305 in subjects with PBC, with or without inadequate response to UDCA. Both males and females may be enrolled in the study, though the condition PBC is mainly found in women (10:1 women versus men). Suspicion of a potential PBC diagnosis is raised by an elevation of alkaline phosphatase (ALP) noted on screening blood tests obtained during routine office visits.

This SAP should be read in conjunction with the study protocol and case report form (CRF). This version of the plan has been developed using the protocol dated 02Apr2018 (Amendment 2.0) and CRF dated 01Aug2018. Any further changes to the protocol or CRF may necessitate updates to the SAP.

Changes following approval of this SAP will be tracked in the SAP Change Log and a final amended version will be issued for Sponsor approval prior to database lock, and subsequent unblinding of treatment codes and efficacy lab data for final study results delivery.

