The total maximum length of time of participation for each subject enrolled in the study will be approximately 20 weeks based on a maximum of 28 days for the Screening Period, 12 weeks for the Treatment Period and 4 weeks for the Follow-up Period.

The planned sample size is approximately 105 subjects. Group sample sizes of 45 in each active arm and 15 in the placebo arm achieve 83.552% power to detect a ratio of the group proportions of 40%. The proportion in the smallest active arm is assumed to be 0.4000 under the null hypothesis and 0.0400 under the alternative hypothesis. The proportion in the placebo arm is 10%. The test statistic used is the two-sided Mantel-Haenszel test. The significance level of the test is 0.05.

To account for a 10% discontinuation rate, 14 additional subjects will be enrolled to attempt to have 105 who complete treatment, bringing the total number of subjects enrolled to 119.

PASS software version 14 was used to calculate the sample size.

Subjects will be asked to participate in the PK/PD substudy. The randomization schedule will be developed to allow for balance between the treatment groups within the substudy. For all non-PK/non-PD analysis purposes, the subjects in the substudy will be combined with the subjects not in the substudy.

In order to achieve this balance subjects will be stratified by:

- 1) prior use of fibrates
- 2) prior and/or current use of UDCA

Note that both 1) and 2) may be applicable for a given subject. In addition, a subset of subjects will be included in the PK/PD substudy.

Subjects will be randomized to 3 treatment groups in a 3:3:1 ratio after stratification:

- Treatment Group 1: EDP-305 1 mg orally for 12 weeks
- Treatment Group 2: EDP-305 2.5 mg orally for 12 weeks
- Treatment Group 3: Placebo (PBO) orally for 12 weeks

A minimum of 10 subjects per treatment group will be included in the PK/PD substudy.

Triangle Biostatistics generated the randomization schedule and provided it to Bioclinica as the IWRS vendor, for incorporation into the IWRS

6 Statistical Considerations

All analyses will use SAS version 9.4 or higher.

Continuous and discrete variables will be summarized using an 8-number summary (n, mean, standard deviation, median, 25th quartile, 75th quartile, minimum and maximum values). The median, minimum and maximum values will be displayed to the same level of precision as the raw data, the mean to one additional decimal place and the SD to two additional decimal places.

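### The subgroup code for ALP response gives one treatment p-value pooled over a factor's levels, and the SAP plans no result for any single level

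*SAP*

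**What the plan says.** SAP 9.1.2 first sets out the primary analysis: "The CMH test will be stratified, two-sided with an alpha level at 0.05". Its PROC FREQ statement is a three-way table with the combined randomization stratum first, treatment second and response third, and the CMH option. By the SAP's own usage, then, the first variable is the stratifier.

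The section goes on: "Subgroup analysis will be performed for ALP Response for the following subgroups". Seven factors follow, with these listed levels:

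- age, 2
- gender, 2
- UDCA stratum, 2
- prior-fibrate stratum, 2
- baseline ALP, 5
- baseline total bilirubin, 3
- combined ALP/bilirubin/UDCA factor, 8

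The code is introduced with "The code used to generate the p-value for each active treatment vs the placebo will be". It is the primary statement again, with the subgroup factor in place of the stratum. No BY or WHERE statement, and no wording, limits it to one level. The section adds that "The subgroup analysis will be performed using the Full Efficacy population" and names no per-level difference, interval or heterogeneity test.

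Elsewhere, SAP 9.1.4 plots ALP values and change from baseline separately by UDCA and fibrate stratum, but not ALP response. SAP 6.4 makes no multiplicity adjustment.

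**The concern.** A subgroup analysis asks whether the effect is present in each level and whether it differs between levels. A CMH test stratified by the factor answers neither question. It estimates one common treatment effect, adjusted for the factor, and here it also drops the adjustment for the randomization strata. A p-value labelled gender would be the overall drug-placebo comparison adjusted for sex.

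The likely misreading is direct. A small p-value beside a factor looks like evidence about its levels, yet it can arise when one level has no effect. A large one can hide a small level that responds. Protocol 4.2.2 says the trial is to support Phase 3, where consistency by UDCA use, prior fibrates and baseline ALP would matter.

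**Working it through.** **What the code returns.** The plan gives no figure for the subgroup analysis to reproduce. The power of 83.552% in SAP 5 concerns the primary comparison and is not used here. Counting from 9.1.2: 2+2+2+2+5+3+8 = 24 levels, and 7 factors × 2 doses = 14 p-values, each pooled over levels. This assumes the input data hold one active arm plus placebo, as the introductory sentence implies.

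**How pooling hides the levels.** In level h, let a of n active patients respond, with m placebo patients, k responders in all and N = n + m. Then

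E = nk/N, V = nmk(N−k)/[N²(N−1)], Q = (Σa − ΣE)²/ΣV on 1 df.

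Example with assumed counts:

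- Level 1, 20/36 vs 1/12: E = 36×21/48 = 15.75; V = 36×12×21×27/(48²×47) = 2.262; Q = 4.25²/2.262 = 7.985, p = 0.0047.
- Level 2, 2/15 vs 1/5: E = 15×3/20 = 2.25; V = 15×5×3×17/(20²×19) = 0.503; Q = 0.25²/0.503 = 0.124, p = 0.7245.
- Pooled: Q = (22 − 18)²/2.765 = 5.786, p = 0.0162.

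The pooled result is significant although the second level shows nothing. With 15/30 vs 1/10 and 1/15 vs 3/5, the level differences are +0.40 (p = 0.027) and −0.53 (p = 0.012). The pooled Q is (16 − 15)²/2.478 = 0.404, p = 0.53.

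**How often this happens.** Inputs:

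- Arm sizes: 119 enrolled at 3:3:1 gives 119/7 = 17 placebo and 51 per active arm.
- Placebo rate: SAP 5 says "The proportion in the placebo arm is 10" percent.
- Active rate: 40%, the 0.4000 in the same paragraph. That sentence is garbled (it gives 0.4000 under the null and 0.0400 under the alternative), so 40% is a reading of it.
- Level splits: assumed, shown as a range. For gender, SAP 3 says "the condition PBC is mainly found in women (10:1 women versus men"), so men number about 51/11 = 4.6 active and 17/11 = 1.5 placebo.

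All possible tables were enumerated exactly. In the second to fourth columns the effect is only in the larger level (40% vs 10%, with 10% vs 10% in the smaller). In the last column it is only in the smaller level.

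| Active split vs placebo split | Pooled p<0.05 favouring drug | Of those, Breslow-Day p<0.05 | Of those, no placebo responder | Pooled p<0.05, effect only in smaller level |
|---|---|---|---|---|
| 26+25 vs 9+8 | 26.6% | 11.5% | 55.8% | 22.8% |
| 31+20 vs 10+7 | 33.5% | 14.4% | 47.1% | 17.6% |
| 36+15 vs 12+5 | 43.2% | 16.2% | 37.7% | 10.4% |
| 41+10 vs 14+3 | 54.0% | 13.4% | 30.7% | 4.7% |
| 46+5 vs 15+2 (gender) | 60.2% | 9.9% | 27.6% | 2.4% |

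With one placebo man instead of two (46+5 vs 16+1), the second to fourth columns are 62.8%, 5.8% and 26.5%.

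The Breslow-Day column counts an undefined statistic as not flagged. The statistic is undefined when placebo has no responder, or when a level has none in either arm. Together these cover 44% to 57% of the significant trials for the first four splits and 63% for gender. Among trials where it can be computed, it is below 0.05 in 26% to 29%, and 27% for gender.

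**What per-level testing could do.** At a true 40% vs 10%, within-level power of the same test is 49% for 36 vs 12, 13% for 15 vs 5 and 1% for 5 vs 2. Intervals are therefore more useful than per-level p-values.

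**The case against.** The code is a template with placeholders. Run literally on three arms it would not give the pairwise p-values the text promises, so some restriction must be implied, and a restriction to one level could be implied too. The text plainly intends analysis by subgroup. PROC FREQ prints the level tables and a Breslow-Day test by default, and SAP 6 says categorical variables are summarized by frequencies and percentages by treatment group. The level count is not fixed either: 16 of the 24 belong to factors marked as data dependent, and inclusion criterion 6 refers to bilirubin below 2×ULN, so upper bilirubin levels may be empty. The scenarios are constructed, 10:1 describes the disease and not planned enrolment, and 40%/10% ignores the discontinuation allowance with missing counted as failure. Finally, no decision rests on subgroups.

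Part of this stands. The splits and the no-effect level are assumptions. If every one of 10% discontinuers is a failure, the rates become 36% and 9%, and the pooled p-value is below 0.05 in 22% to 47% of trials (52% for gender). Neither point removes the structural fault. Restricting the data to one level would make the subgroup term redundant, and the SAP does not ask for it. Default printed output is not a commitment to report, and the general rule in SAP 6 does not say per level. Low within-level power argues for descriptive intervals, not for a pooled p-value.

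**Conclusion.** The concern holds. As written, SAP 9.1.2 produces a factor-adjusted overall treatment p-value for each factor and dose, and commits to no per-level or heterogeneity result for ALP response. This follows from the code's form and needs no numerical assumption beyond the pairing of one active arm with placebo.

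The size does depend on assumptions. With 51 vs 17 patients, 40% vs 10% in the larger level and no effect in the smaller, the pooled p-value favours drug at p<0.05 in 27% to 54% of trials, and in 60% at the gender split. With the effect only in the smaller level it is below 0.05 in 23% down to 5%, and 2% for gender.

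The primary analysis is untouched, so this should be corrected but does not threaten the main result. One limit: Appendix 4, which the SAP cites for interim and DSMB outputs, is not in the supplied text, so the finding concerns section 9.1.2.

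**What to change.** For each active-placebo pair, run the comparison by level, for example with `BY subgroup` and a two-way table of treatment by response. For each level report n (%) responders per arm and the difference with a 95% CI suited to small counts, such as Newcombe or exact. Label the subgroup results descriptive, and do not present the pooled CMH p-value as subgroup evidence. A heterogeneity test may be added per factor where it can be computed, with a note that it has little power and is undefined when placebo has no responders.

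This costs a few lines of SAP text and code, and should be done before unblinding. The price is more output and wide intervals. By Newcombe, 14/36 vs 1/12 gives +31 points (0 to +48), and 2/5 vs 0/2 gives +40 points (−32 to +77). That width is an honest picture of what so small a placebo arm can show.

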9.1.3 Imputation of Missing Data

To account for missing data, a sensitivity analysis will be performed using the multiple imputation Markov Chain method.

MMRM Using Multiple imputation (MI)

To assess robustness of the efficacy analysis, sensitivity analysis with missing values imputed by MI will be performed on ALP change from baseline data. In the first stage, missing values will be imputed by Markov Chain Monte Carlo (SAS PROC MI, MCMC) to make the missing pattern monotone (by filling in

imputed values of ALP between 2 non-missing values). In the second stage, monotone linear regression will fill in missing values through Week 12. SAS PROC MI and PROC MIXED will be used to obtain MMRM estimates of treatment difference. SAS PROC MIANALYZE will be used to combine estimates and to generate the average test statistics for hypothesis testing. The Missing at Random method will be used with the following parameters MAR – assume missing at random, number of imputation=100, seed=SEED11 (for MCMC) and SEED12 (for MONOTONE REG) for imputation.

